6.3 Data Monitoring Committee

An internal safety DMC composed of persons independent of the RCT Study M19-130 and LTE Study M20-186 teams and with relevant expertise in their field will review unblinded safety data. The primary responsibility of the DMC will be to protect the safety of the subjects participating in this LTE study. When needed, high-level unblinded efficacy data may also be requested by the DMC and reviewed so that the DMC can assess benefit/risk of any emerging safety differences.

A separate DMC charter for LTE Study M20-186 is available and describes the roles and responsibilities of the DMC members, frequency of data reviews, planned interim analyses, relevant safety data to be assessed, and expectations for blinded communications for LTE Study M20-186.

7 STATISTICAL METHODS & DETERMINATION OF SAMPLE SIZE

7.1 Statistical and Analytical Plans

Complete and specific details of the statistical analysis will be described and fully documented in the Statistical Analysis Plan (SAP). The SAP will be finalized prior to the database lock. The statistical analyses will be performed using SAS (SAS Institute Inc., Cary, North Carolina, USA).

7.2 Definition for Analysis Populations

The Full Analysis Set (FAS) includes all subjects received at least 1 dose of study drug in LTE Study M20-186. The FAS will be used for efficacy and baseline analyses. Subjects will be grouped according to treatment sequence as randomized for Studies M19-130 and M20-186.

The Safety Analysis Set includes all subjects who received at least 1 dose of study drug in LTE Study M20-186. Subjects will be grouped according to treatment sequence actually received. The Safety Analysis Set will be used for safety analyses.

7.3 Statistical Analyses for Efficacy

Analysis of secondary efficacy endpoints will be conducted on the FAS based on treatment sequence as randomized for Study M19-130 and continued/reassigned to rollover into LTE Study M20-186. The analysis will be based on As Observed (AO) data, and no imputation will be conducted. The treatment groups will be described as follows whenever applicable indicating treatments from Study M19-130 to LTE Study M20-186:

- Group 1: Elsubrutinib 60 mg / upadacitinib 30 mg to elsubrutinib 60 mg / upadacitinib 30 mg
- Group 2: Elsubrutinib 60 mg / upadacitinib 15 mg to elsubrutinib 60 mg / upadacitinib 15 mg
- Group 3: Elsubrutinib 60 mg to elsubrutinib 60 mg
- Group 4: Upadacitinib 30 mg to upadacitinib 30 mg
- Group 5a: Placebo to elsubrutinib 60 mg / upadacitinib 30 mg
- Group 5b: Placebo to elsubrutinib 60 mg / upadacitinib 15 mg

The Baseline for all secondary efficacy analyses in this study will be the Baseline in Study M19-130.

There is no primary efficacy endpoint and no formal statistical tests will be applied. Only descriptive statistics will be used for all efficacy endpoints. Descriptive statistics will be provided for each treatment group for all visits. These include the number of observations; mean with 95% confidence interval, standard deviation, median, minimum, and maximum for continuous endpoints (or the change from baseline measurements); and frequencies and percentages with 95% confidence interval for binary endpoints.

No missing data imputation will be applied. All efficacy analyses will be based on AO analysis, and thus a subject who does not have an evaluation at the analysis time point will not be included. Missing value/visit information due to COVID-19 will be collected and reported.

Details on other efficacy analyses will be provided in the SAP.

7.4 Statistical Analyses for Safety

All safety analyses will be performed on the Safety Analysis Set.

All treatment-emergent adverse events (TEAEs), SAEs, AEs leading to discontinuation, and AESI will be collected during the study. A TEAE is defined as an event with onset or worsening after the first study dose of study drug and within 30 days after the last dose of study drug administration. The number and percentages of subjects experiencing TEAEs will be tabulated using the Medical Dictionary for Drug Regulatory Activities (MedDRA®) System Organ Class (SOC) and preferred term (PT). Summaries (including percentages and events per 100 patient-years) of SAEs, deaths, AEs leading to discontinuation, and AESI will be provided as well. For selected laboratory and vital sign parameters, mean change from Baseline and the percentage of subjects with evaluations meeting pre-defined criteria for Potentially Clinically Important values will be summarized.

7.5 Interim Analysis

An interim analysis may be performed as needed in order to provide long-term safety data to inform the benefit-risk assessment of elsubrutinib, upadacitinib, and ABBV-599 (elsubrutinib/upadacitinib) combination. All endpoints will be summarized using descriptive statistics, and summaries will be displayed both overall and split by treatment groups indicating treatments from Study M19-130 to LTE Study M20-186. The detailed interim analysis plan will be provided in the SAP.

7.6 Overall Type I Error Control

Not applicable for this study.

7.7 Sample Size Determination

The sample size will be determined by the number of available subjects who were randomized into Study M19-130 and are eligible for the current study. All eligible subjects who completed Study M19-130 will be enrolled in this study if the subject signs and dates the informed consent. It is anticipated that between 60% and 80% of subjects from Study M19-130 (195 to 260 subjects) will be enrolled in this LTE study.

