| | Achievement of 50% reduction in Cutaneous Lupus Erythematosus Disease Area and Severity Index (CLASI) activity score (of those starting with CLASI ≥ 10 at M19-130 Baseline) | | |
| | 5. Change in SLEDAI-2K from M19-130 Baseline | | |
| | 6. Change in BILAG from M19-130 Baseline | | |
| | Change in Physician's Global Assessment (PhGA) from M19-130 Baseline | | |
| | 8. Change in Patient Global Assessment (PtGA) from M19-130 Baseline | | |
| | Change in Functional Assessment of Chronic Illness Therapy (FACIT)-Fatigue from M19-130 Baseline | | |
| | Change in 36-Item Short Form Health Survey (SF-36) from M19-130 Baseline | | |
| _ | 11. Change in Lupus Quality of Life questionnaire (LupusQoL) from M19-130 Baseline | | |

| | Change in Pain Numerical Rating Scale (NRS) from M19-130 Baseline Number of withdrawals from study drug due to lack of efficacy Safety Endpoints: The following safety evaluations will be performed for the entire study duration as measures of safety and tolerability: | |
|--|--|--|
| Investigator(s): | Multicenter | |
| Study Site(s): | Approximately 100 sites including, but not limited to, Argentina, Australia, Canada, China, Colombia, France, Germany, Hungary, Italy, Japan, Mexico, Netherlands, New Zealand, Poland, South Korea, Spain, Taiwan, the United Kingdom, and the United States (including Puerto Rico). | |
| Study Population and Number of Subjects to be Enrolled: | Adult subjects with SLE who have completed the M19-130 Phase 2 study while on study drug and have not developed any laboratory or clinical discontinuation criteria as defined in that study. Based on the planned Study M19-130 Interim Analysis, 1 or more treatment groups may be discontinued. Subjects that are part of the discontinued treatment group(s) will not be eligible for this study. It is anticipated that between 60% and 80% of subjects from Study M19-130 (195 to 260 subjects) will be enrolled in this study. | |

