4 INVESTIGATIONAL PLAN

4.1 Overall Study Design and Plan

This is a multicenter, double-blind LTE Phase 2 study to investigate the longer-term safety and efficacy of elsubrutinib and upadacitinib given alone or as the ABBV-599 (elsubrutinib/upadacitinib) combination in subjects with moderately to severely active SLE. The study population will consist of approximately 195 to 260 individuals with moderately to severely active SLE despite standard of care therapy.

Subjects who participated in Study M19-130 may be offered the opportunity to consent for this study. The number of subjects participating in this study will not be greater than the number randomized into Study M19-130. Subjects discontinuing study drug prematurely in Study M19-130 are not eligible to participate in the LTE study.

In Study M19-130, subjects were randomized in a 1:1:1:1:1 ratio to one of 5 treatment groups:

- Elsubrutinib 60 mg once a day (QD) and upadacitinib 30 mg QD (projected n = 65)
- Elsubrutinib 60 mg QD and upadacitinib 15 mg QD (projected n = 65)
- Elsubrutinib 60 mg QD and upadacitinib placebo QD (projected n = 65)
- Elsubrutinib placebo QD and upadacitinib 30 mg QD (projected n = 65)
- Elsubrutinib placebo QD and upadacitinib placebo QD (projected n = 65)

Prior to the planned Study M19-130 Interim Analysis, qualified subjects entering into LTE Study M20-186 stayed in their original treatment group from Study M19-130 if on an ABBV-599 (elsubrutinib/upadacitinib) combination, elsubrutinib 60 mg monotherapy, or upadacitinib 30 mg monotherapy. Those originally assigned to the placebo group in Study M19-130 were randomized centrally in a 1:1 ratio to the 2 ABBV-599 (elsubrutinib/upadacitinib) combination treatment groups.

Prior to the planned Study M19-130 Interim Analysis, there were 4 treatment groups in this LTE study:

- Group 1: Elsubrutinib 60 mg QD and upadacitinib 30 mg QD
- Group 2: Elsubrutinib 60 mg QD and upadacitinib 15 mg QD
- Group 3: Elsubrutinib 60 mg QD and upadacitinib placebo QD
- Group 4: Elsubrutinib placebo QD and upadacitinib 30 mg QD

A planned unblinded interim analysis for Study M19-130 was scheduled when 50% of the planned subjects completed their Week 24 assessments. The objective of this analysis was to reassess the treatment regimens in Study M19-130 and the benefit/risk for rollover into LTE Study M20-186.

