The Study M19-130 Interim Analysis was performed by an independent team at AbbVie that was separate and apart from the blinded study team for Study M19-130. The M19-130 study team will remain blinded through the Study M19-130 Week 24 Primary Analysis.

An Interim Unblinding Plan (IUP) was developed separately describing the analyses to be performed and included execution logistics, an unblinded analysis team, and the data chain of custody to protect the integrity of the study.

An Internal Executive Review Committee (IERC) reviewed the interim unblinded results as specified in the IERC charter and decided which treatment group(s) should be continued in Study M19-130 and for rollover into LTE Study M20-186. Study sites and subjects remained blinded to treatment assignment in Study M19-130 and LTE Study M20-186 throughout the studies.

Based on the benefit/risk assessment of the planned Study M19-130 Interim Analysis, subjects in 1 or more groups of LTE Study M20-186 may be discontinued. Subjects in any discontinued group(s) should return for a Premature Discontinuation (PD) visit and have a follow-up phone call 30 days after the last study drug dose.

Subjects originally assigned to the placebo group in Study M19-130 will be rolled over and will be randomized to an active treatment group in LTE Study M20-186.

[figure not shown]
This study includes a 56-week double-blind treatment period with study visits conducted at Weeks 48, 56, 64, 72, 80, 88, 96, and 104 (from the Baseline visit of Study M19-130), and a subsequent telephone follow-up call 30 days after the last visit to determine the status of any ongoing AEs/SAEs or the occurrence of any new AEs/SAEs. The plan is to extend the trial if data support the safety and efficacy endpoints during the 56-week LTE study duration.

An interim analysis for LTE Study M20-186 may be performed to aid data interpretation and to facilitate interactions with regulatory authorities.

The schematic of the study is shown in Figure 1. Further details regarding study procedures are located in the Operations Manual (Appendix H). See Section 5 for information regarding eligibility criteria.

Figure 1. Study Schematic

QD = once daily

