4.2 Discussion of Study Design

Choice of Control Group

There will not be any placebo control in LTE Study M20-186. Subjects in LTE Study M20-186 will roll over from Study M19-130. The objective of this LTE study is to evaluate longer-term safety and tolerability of elsubrutinib, upadacitinib, and ABBV-599 (elsubrutinib/upadacitinib) combination in SLE, and thus the primary comparison will be relative to the safety profile observed in each treatment group during the initial randomized study.

Appropriateness of Measurements

Standard statistical, clinical, and laboratory procedures will be utilized in this study. All safety and efficacy measurements in this study are standard for assessing disease activity in subjects with SLE being treated with immunosuppressive therapies. All clinical and laboratory procedures in this study are standard and generally accepted.

Suitability of Subject Population

After the planned Study M19-130 Interim Analysis, this rollover LTE study will enroll subjects who have successfully completed 48 weeks of treatment in Study M19-130 on placebo or a treatment group that is still active. Only those subjects who have met all of the specified eligibility criteria will have an option to

enter the LTE study to receive continued therapy, provided the subject is willing and the investigator believes that continuing therapy is appropriate.

Selection of Doses in the Study

The dose selection in Study M19-130 was based on analysis of pharmacokinetic, pharmacodynamic, safety, and efficacy (upadacitinib only) data from Phase 1 studies in healthy volunteers for elsubrutinib, Phase 2 and Phase 3 studies for upadacitinib in RA, as well as a published study of baricitinib in SLE.⁸⁻¹⁰

The 60 mg dose of elsubrutinib is intended to target exposures at or greater than those needed to achieve maximal peripheral BTK occupancy. Following QD dosing of elsubrutinib 60 mg, peak and trough BTK occupancy at steady-state are predicted to be 99% and 89%, respectively. Furthermore, the elsubrutinib dose of 60 mg (administered alone or with upadacitinib 30 mg) has been shown to be safe and well-tolerated in Phase 1 studies in healthy subjects.

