2.2 Study Design Overview

This is a double-blind LTE Phase 2 study to investigate the longer-term safety and efficacy of elsubrutinib and upadacitinib given alone or as the ABBV-599 (elsubrutinib/upadacitinib) combination in subjects with moderately to severely active SLE. The study population will consist of approximately 195 to 260 individuals who entered Study M19-130 with moderately to severely active SLE despite standard of care therapy and who have completed Study M19-130.

The schematic of the study is shown in [Figure 1](#).

Figure 1. Study Schematic

QD = once daily

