2.3 Treatment Assignment and Blinding

Prior to the planned Study M19-130 Interim Analysis, qualified subjects entering into LTE Study M20-186 stayed in their original treatment group from Study M19-130 if on

an ABBV-599 (elsubrutinib/upadacitinib) combination, elsubrutinib 60 mg monotherapy, or upadacitinib 30 mg monotherapy. Those originally assigned to the placebo group in Study M19-130 were randomized centrally in a 1:1 ratio to the 2 ABBV-599 (elsubrutinib/upadacitinib) combination treatment groups.

Prior to the planned Study M19-130 Interim Analysis, there were 4 treatment groups in this LTE study:

- Group 1: Elsubrutinib 60 mg QD and upadacitinib 30 mg QD
- Group 2: Elsubrutinib 60 mg QD and upadacitinib 15 mg QD
- Group 3: Elsubrutinib 60 mg QD and upadacitinib placebo QD
- Group 4: Elsubrutinib placebo QD and upadacitinib 30 mg QD

A planned unblinded interim analysis for Study M19-130 was performed when 50% of the planned subjects completed their Week 24 assessments. The objective of this analysis was to reassess the treatment regimens in Study M19-130 and the benefit/risk for rollover into Study M20-186.

Based on the benefit/risk assessment of the planned Study M19-130 Interim Analysis, subjects in 1 or more groups of LTE Study M20-186 may be discontinued. Subjects in any discontinued group(s) should return for a Premature Discontinuation (PD) visit and have a follow-up phone call 30 days after the last study drug dose.

This study includes a 56-week double-blind treatment period with study visits conducted at Weeks 48, 56, 64, 72, 80, 88, 96, and 104 (from the Baseline visit of Study M19-130), and a subsequent telephone follow-up call 30 days after the last visit to determine the status of any ongoing AEs/SAEs or the occurrence of any new AEs/SAEs. The plan is to extend the trial if data support the safety and efficacy endpoints during the 56-week LTE study duration.

The M19-130 Primary Analysis will be performed when all subjects have completed the Week 24 visit. The M20-186 study team will become unblinded after the M19-130

Week 24 Primary Analysis has been completed. Study sites and subjects will remain blinded to treatment assignment in Study M19-130 and Study M20-186 throughout the studies.

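### Should the anticipated enrolment of 195 to 260 be cut because subjects in discontinued M19-130 groups cannot enter?

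*Protocol*

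**What the plan says.** The same range appears in five places: Protocol Sections 1, 4.1 and 7.7, and SAP Sections 2.2 and 2.4. Section 7.7 puts it this way: "It is anticipated that between 60% and 80% of subjects from Study M19-130 (195 to 260 subjects) will be enrolled in this LTE study". SAP 2.2 repeats it: "The study population will consist of approximately 195 to 260 individuals who entered Study M19-130". SAP 2.4 attributes the 60–80% share to efficacy-based discontinuation criteria in the feeder study.

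Protocol 4.1 lists five M19-130 groups randomized equally, each with the same projected size; the last entry is "Elsubrutinib placebo QD and upadacitinib placebo QD (projected n = 65").

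Three statements bear on who can enter:

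- The synopsis says that one or more groups may be discontinued after the M19-130 interim analysis, and continues: "Subjects that are part of the discontinued treatment group(s) will not be eligible for this study".
- Protocol 4.2 limits entry after that analysis to subjects who "completed 48 weeks of treatment in Study M19-130 on placebo or a treatment group that is still active".
- Protocol 4.1 reports that an internal committee "decided which treatment group(s) should be continued in Study M19-130 and for rollover into LTE Study M20-186".

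The opening sentence of Protocol 7.7 makes the sample size the number of M19-130 subjects who are available and eligible. Protocol 7.2 says the Safety Analysis Set "includes all subjects who received at least 1 dose of study drug in LTE Study M20-186".

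**The concern.** The forecast and the eligibility rule appear to use different populations. The range is a share of every projected M19-130 subject, but after the interim analysis only placebo subjects and those in continuing groups can enter. The reason SAP 2.4 gives for the 60–80% share concerns discontinuation criteria within M19-130. Closing a whole group would be a further loss, and no allowance for it is stated.

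Timing makes this look like an oversight. The protocol synopsis is dated 26 October 2021 and reports the interim review as done. The protocol's summary of changes says groups were selected to move forward on efficacy results. SAP version 2.0 (02 January 2024) was updated to align with the protocol after that analysis. Both kept the number.

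The primary objective is longer-term safety, this is the only anticipated study size, and SAP 9.2.2 summarises treatment-emergent adverse events overall as well as by group. A reader who took 195 to 260 as the pooled size might expect tighter bounds on uncommon events than the study would deliver.

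**Working it through.** **Inputs.** Five groups, projected 65 each (Protocol 4.1). Rollover share r = 0.60 to 0.80 (Protocol 7.7). Interim timing from SAP 2.3: "A planned unblinded interim analysis for Study M19-130 was performed when 50% of the planned subjects completed their Week 24 assessments". The number of closed groups, k, is not given, so k = 1 and k = 2 are assumptions.

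**The plan's own figure.** 5 × 65 = 325; 0.60 × 325 = 195 and 0.80 × 325 = 260. Both ends are exact, so the base is all five groups.

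**Effect of closing groups.** Let f be the fraction of a closed group's rollovers who entered the extension before closure. Then

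N = r × 65 × (5 − k + f × k).

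A ceiling on early entry at the interim cut-off also follows. Entry requires Week 48, and only half of the planned subjects had completed Week 24. Half of 325 is 162.5, or about 32 per group if groups were balanced. The ceiling is therefore N = r × 65 × (5 − k) + 32k. Entry between the cut-off and closure would add to it.

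| Groups closed | No early entrants (f = 0) | f = 0.5 | Ceiling at cut-off |
|---|---|---|---|
| 0 | 195–260 | – | – |
| 1 | 156–208 | 176–234 | 188–240 |
| 2 | 117–156 | 156–208 | 181–220 |

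With f = 0, reaching 195 needs 195/260 = 75% rollover for one closure and 195/195 = 100% for two. At 70% rollover, 195/(0.7 × 65) = 4.29 groups' worth of subjects are needed. That means f = 4.29 − 4 = 0.29 for one closure, or (4.29 − 3)/2 = 0.64 for two.

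**Effect on precision.** The one-sided 95% upper bound when no event is seen is 1 − 0.05^(1/N).

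| Case | N | Bound |
|---|---|---|
| None closed | 195–260 | 1.5%–1.1% |
| One closed, f = 0 | 156–208 | 1.9%–1.4% |
| Two closed, f = 0 | 117–156 | 2.5%–1.9% |
| One closed, ceiling | 188–240 | 1.6%–1.2% |
| Two closed, ceiling | 181–220 | 1.6%–1.4% |

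For a continuing active group, 0.60 × 65 = 39 and 0.80 × 65 = 52. The bound is 1 − 0.05^(1/39) = 7.4% to 1 − 0.05^(1/52) = 5.6%, whether or not another group closed.

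**What uses the number.** Protocol Section 3 plans no hypothesis, Protocol 7.6 says type I error control does not apply, and neither document derives a precision target from 195 to 260. Protocol 4.2 makes the main safety comparison each group against its own profile in M19-130. SAP 5.0 reports actual enrolment by group, and SAP 9.2.4 uses actual exposure for event rates.

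**The case for a change.** The best argument for a change is that the mismatch is verifiable, survived two post-interim revisions, and could be cured by wording alone. Even at the cut-off ceiling, 260 is out of reach at 60–80% rollover once a group has closed. Headcount also flatters the information available: subjects from a closed group who entered early are called back for a premature discontinuation visit, so they count as enrolled but may contribute well under 56 weeks.

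Most of this stands as description. The base is all five groups, no allowance for closure is stated, and the upper end would be optimistic if a group closed. It does not stand as proof of a wrong figure. The documents say that groups may be discontinued and that groups were selected to go forward; they do not say that any closed, or how many. If none closed, the range is right. The feeder-study criteria behind the 60–80% are also not in these documents, so whether the share leaves room for other losses is a matter of inference.

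The remedy costs more than it first seems. Revising the protocol is an amendment needing ethics approval (Protocol 8.1) across approximately 100 sites. A revised total could also hint at how many groups closed, while sites and subjects are meant to stay blinded.

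**Conclusion.** No change is needed, because a change would gain nothing. The range is an expectation computed correctly on all five projected groups. It is too high only if one or more groups closed, and then by an amount the documents do not allow anyone to calculate: from 156–208 to about 188–240 for one closure, and from 117–156 to about 181–220 for two. These figures assume 65 per group, 60–80% rollover, and either no early entry or the balanced-group ceiling at the interim cut-off.

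The eligibility rule already governs who enters. Section 7.7 sets the sample size by availability and eligibility, and the synopsis places the exclusion next to the forecast. Restating the range would alter no enrolment, analysis, result or conclusion. A continuing active group still expects 39 to 52 subjects, and the report will show the true numbers and exposure. If the SAP is reopened for another reason, a clause noting that 195 to 260 assumes all five groups continue would be harmless, but the point does not warrant a revision by itself.
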